## 4.5 Exposure

### 4.5.1 Exposure Days and Time on Study

Exposure days (EDs) and time on study will be summarized for the Safety, Efficacy, Surgery and CCI population. Exposure for subjects coming from the pivotal studies (1001, 3002) will also be assessed cumulatively.

An ED is defined as any day that the subject receives an injection of rVIII-SingleChain regardless of the number of injections on that day. Total EDs are cumulative from previous pivotal study for PTPs in Arm 1 and are calculated from the first dose of rVIII-SingleChain, including all EDs to rVIII-SingleChain from any study or the surgical component of this study.

CCI

The number of EDs will be summarized as both a continuous and categorical variable by age group as defined in this section.

The following categories will be presented, based on first day of dosing in the pivotal study for Arm 1 and in this study for Arm 2 and Arm 3:

- PTPs: 0-10 EDs, >10-15 EDs, >15-50 EDs, >50-75 EDs, >75-100 EDs, >100 EDs
- PUPs: 0-10 EDs, >10-25 EDs, >25-50 EDs, > 50 EDs

Exposure days in the current study will be summarized as well, as both a continuous and categorical variable as described above. EDs in the current study are counted from first dose in this study or the surgical component of this study or the CCI [REDACTED]

Total time on study (days) will be derived as:

$[Maximum \text{ (rVIII-SingleChain last dose date, End of study visit date)}] - [Minimum \text{ (rVIII-SingleChain first dose date considering pivotal study for PTPs Arm 1, Day 1 date in the current study)}] + 1.$

Time on current study (days) will be derived as:

$[Maximum \text{ (rVIII-SingleChain last dose date, End of study visit date)}] - [Minimum \text{ (rVIII-SingleChain first dose date during the current study, Day 1 date in the current study)}] + 1.$

Total time on study and time on current study in days, weeks (days/7), and months (days/30.4375) will be summarized using descriptive statistics. Time on study will be described with statistics for continuous variables. Total subject-years will be provided.

CCI [REDACTED]

ED will also be summarized by Inhibitor Level (high/low titer) on PUPs.

In addition, a separate exposure analysis over the period of inhibitor development will be provided while subjects are inhibitor positive on PUPs.

CCI [REDACTED]

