1.4 Potential Risks and Benefits

The risks include the possibility that subjects treated with rVIII-SingleChain may develop an inhibitor and that antihemophilic factors may therefore be less effective or ineffective in increasing FVIII levels and stopping or preventing bleeding. Treatment with any antihemophilic factor presents a risk of inhibitor formation particularly in PUPs in which the risk of inhibitor formation has been estimated to be up to 35.4% [SIPPET study, [Peyvandi et al., 2016](#); [Kasper, 2004](#)]. The development of an inhibitor is associated with significant morbidity and mortality, including a higher rate of bleeding complications, increased disability and a decreased quality of life [[Witmer and Young, 2013](#)]. The absolute risk of inhibitor formation with rVIII-SingleChain is currently unknown. In Study CSL627_1001 in 174 PTPs with previous exposure to > 150 EDs to FVIII products, 120 subjects achieved ≥ 50 EDs, of whom 52 subjects had ≥ 100 EDs to rVIII-SingleChain at the end of the study.

CCI [Redacted]

CCI [Redacted]

For subjects in all study arms, the potential benefits of treatment include stopping and / or preventing bleeding. In addition, rVIII-SingleChain has demonstrated an adequate safety profile for PTPs. The associated benefit-risk assessment of the study is acceptable for subjects enrolled.

Please refer to the Investigator’s Brochure for more detailed information.

2 Study Objectives and Endpoints

Overall, the study objectives in all 3 study arms are to gain additional safety information on the incidence of FVIII inhibitors (including in PUPs), frequency of adverse events (AEs), and serious AEs (SAEs) associated with the use of rVIII-SingleChain, and to gain additional information on the efficacy of rVIII-SingleChain in PTPs and PUPs with severe hemophilia A. This study will collect information on subjects undergoing surgery during the study, thereby providing information on the safety and efficacy of rVIII-SingleChain during surgery. CCI

[REDACTED]

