8.6.2 Blood Samples for Incremental Recovery

In Arms 1 and 3 (PTPs), IR will be collected at Day 1 and at the closest visits after 10 EDs, after 50 EDs, and after 100 EDs, as outlined in [Table 8](#). Incremental recovery ($[\text{IU/mL}] / [\text{IU/kg}]$) is defined as FVIII activity (IU/mL) obtained 30 to 60 minutes following injection, per dose of (IU/kg) injection. Incremental recovery values will be baseline-corrected for pre-injection plasma FVIII activity.

If possible, subjects should have a 4-day washout from their last FVIII infusion before the IR samples are drawn. A pre-dose blood sample will be drawn. Subjects will then receive their prophylaxis dose of rVIII-SingleChain injection. For on-demand subjects, the usual dose used to treat a bleeding episode may be administered or any other dose determined by the investigator. A post-dose blood sample will be drawn 30 to 60 minutes (± 5 minutes) after the injection. The exact times of blood draws and the actual dose (IU/kg actual potency) administered will be recorded. Blood sample collection timepoints are presented in [Table 8](#).

Table 8: Blood sample collection timepoints for inhibitor and incremental recovery assessment (Arms 1 and 3 [PTPs])

	Day 1	Exposure days of rVIII-SingleChain ^A		
		10 EDs	50 EDs	100 EDs
Inhibitor ^B	From previous End of Study Visit	X	X	X
Incremental Recovery ^C	X	X	X	X

Abbreviations: CHO = Chinese hamster ovary; ED = exposure day; PTP = previously treated patient; rVIII = recombinant factor FVIII.

From “Guideline on the clinical investigation of recombinant and human plasma-derived factor VIII products” (EMA, 2011)

- A: For Arm 1, exposure days are cumulative from previous lead-in studies (calculated from the first dose of rVIII-SingleChain in any study). For Arm 3, exposure days will be calculated from the first dose of rVIII-SingleChain in the present study only.
- B: After 4-day washout period (if possible), inhibitor assessment will include inhibitors to FVIII, antibodies against rVIII-SingleChain, and antibodies against CHO proteins.
- C: After 4-day washout period (if possible), blood samples will be drawn: 1) prior to injection of rVIII-SingleChain, and 2) at 30 to 60 minutes (\pm 5 minutes) following injection. The exact times of blood draws post-injection will be recorded.

CCI

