#### 4.1.1.4 Baseline and Changes from Baseline

Baseline is defined as the last assessment before the first dose of rVIII-SingleChain in this study. Measurements obtained after the first dose of rVIII-SingleChain will be considered post-baseline values. If measurement of a variable is not made on a given subject before the first dose of rVIII-SingleChain, then that subject will be considered not to have a baseline value for that variable. Change from baseline will be defined as post-baseline assessment minus baseline assessment.

- CCI
- For the surgical substudy, baseline is defined as the last assessment before the first dose of rVIII-SingleChain for surgery.

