#### 4.7.1 Incidence of Inhibitor Formation

The incidence of inhibitor formation to FVIII will be estimated for subjects in the Safety population who did not have inhibitors at baseline. Baseline assessments are defined as those assessments done before date and time or on the same date and time of the first dose. If time of inhibitors assessment or time of first dose is missing then the inhibitor result taken at the same date of the first dose will be considered as baseline. Inhibitor formation will be defined as any post-baseline inhibitor titer  $\geq 0.6$  BU/mL identified and confirmed by re-testing at a subsequent visit. Both tests must be performed by a central laboratory. A positive result not confirmed as positive by re-testing at a subsequent visit result will be considered as non positive. In the KM analysis of inhibitor occurrence, the first positive result will be considered as an event. A positive result not confirmed as positive by re-testing at a subsequent visit result will not be considered as an event. Positive FVIII inhibitors will be further categorized as low or high titer. Low-titer inhibitors are defined as positive inhibitors with a titer of  $\leq 5$  BU/mL. High-titer inhibitors are defined as positive inhibitors with a titer of  $> 5$  BU/mL.

For the inhibitor incidence after 10 Total EDs, the numerator will include all subjects with inhibitors observed at the closest visit up to 10 EDs ( $\leq 10$  EDs). The denominator will include all subjects with at least 10 EDs ( $\geq 10$  EDs) plus subjects with less than 10 EDs but with inhibitors.

- Numerators = Number of PTP subjects who develop inhibitors up to 10 EDs ( $\leq 10$  EDs)
- Denominators = Total number of PTPs with at least 10 EDs ( $\geq 10$  EDs) + subjects with less than 10 EDs with inhibitors. Subjects not tested at  $\leq 10$  EDs will be excluded.

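### For Arm 1, exposure days start at the first lead-in dose while the default inhibitor baseline starts in this study; on that reading the 50- and 100-ED incidence misses lead-in inhibitors, and SAP 4.7.1 should set one origin

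*SAP*

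**What the plan says.** **Exposure clock.** SAP 4.5.1: "Total EDs are cumulative from previous pivotal study for PTPs in Arm 1 and are calculated from the first dose of rVIII-SingleChain". Protocol 8.6.2 (footnote to Table 8) agrees: "For Arm 1, exposure days are cumulative from previous lead-in studies (calculated from the first dose of rVIII-SingleChain in any study". Arm 3 counts EDs in this study only.

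**Baseline and risk set.** SAP 4.1.1.4: "Baseline is defined as the last assessment before the first dose of rVIII-SingleChain in this study". SAP 4.1.1.1 likewise dates safety findings from the first dose in this study. SAP 4.7.1 then says: "The incidence of inhibitor formation to FVIII will be estimated for subjects in the Safety population who did not have inhibitors at baseline". Its own baseline sentence does not name the study: "Baseline assessments are defined as those assessments done before date and time or on the same date and time of the first dose".

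**Event.** SAP 4.7.1: "Inhibitor formation will be defined as any post-baseline inhibitor titer" at or above 0.6 BU/mL, confirmed on re-test by the central laboratory.

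**Denominator.** At each landmark: subjects who reached it, plus those who developed an inhibitor before it. There is an exclusion, worded at the first landmark as "Subjects not tested at $\leq 10$ EDs will be excluded", with the same form at 50 and 100. Whether tests from the lead-in studies count is not stated.

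**Also planned.** SAP 4.7.1 adds a summary at 10, 50 and 100 EDs counted in the current study.

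**The concern.** A rollover's lead-in EDs count towards the landmark, but on the default baseline an inhibitor that arose during those EDs cannot count as an event. If it was still present at entry, the subject is removed as baseline-positive. If it had resolved, it is not post-baseline. Inhibitor-free rollovers keep all their lead-in EDs. This is delayed entry without an adjustment for it.

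The baseline filter does not come from the protocol. Protocol 11.3.3.2 puts every subject who develops an inhibitor in the numerator, and Protocol 11.1 counts the 100 EDs across all the sponsor's studies of the product. If exposure is pooled, events should be pooled too. SAP 4.11, which lists departures from the protocol, does not mention the filter. Nor is it an empty rule: Arm 1 has no inhibitor exclusion (Protocol 4.1.2.1), whereas Arm 3 excludes any inhibitor history (Protocol 4.1.2.3).

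At stake are the primary PTP safety endpoint (100 EDs) and the secondary incidences at 10 and 50 EDs.

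**Working it through.** **Plan's own figure.** There is none to reproduce. Protocol 11.1 states that no sample size calculation was made and takes 200 PTPs from a guideline.

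**Inputs from the documents.** Protocol 1.4 on CSL627_1001 (174 PTPs): "120 subjects achieved ≥ 50 EDs, of whom 52 subjects had ≥ 100 EDs to rVIII-SingleChain at the end of the study". That gives 174 − 120 = 54 below 50 EDs (31%), 120 − 52 = 68 at 50 to 99 (39%) and 52 at 100 or more (30%). Protocol 1.2.3: CSL627_3002 had 84 subjects, expected to reach at least 50 EDs. How many rolled over, their EDs at entry and the number of lead-in inhibitors are not given.

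**Step 1: three readings of SAP 4.7.1.**

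| Reading | 10 EDs | 50 and 100 EDs |
|---|---|---|
| A. This-study baseline; lead-in tests satisfy the tested rule | low | low |
| B. This-study baseline; lead-in tests before entry do not satisfy it | Arm 1 largely drops out; rests on Arm 3 | still low |
| C. Baseline at first dose ever; lead-in results pooled | no clock mismatch | no clock mismatch |

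Reading B remains low at 100 EDs because a subject entering at, say, 60 EDs has a Day 1 value (taken from the lead-in End of Study visit) below 100 EDs. He stays in the denominator but is at risk only for the last 40.

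**Step 2: zero-event confidence limit.** With no inhibitors the plan reports a one-sided 97.5% limit, U = 1 − 0.025^(1/n).

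- n = 200: U = 1.83%
- n = 148 (200 − 52, if all 52 rolled over and are dropped): U = 2.46%
- n = 100: U = 3.62%; n = 50: U = 7.11%. These would apply at 50 EDs if 100 or 150 of 200 entered past 50 EDs (an assumed range).

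Using n = 200 for such subjects requires Reading A. Under Reading B they are already excluded.

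**Step 3: how low the estimate could be.** Assumptions, none from the documents: 2% true risk by 100 EDs, constant per ED; 75% of PTPs in Arm 1; the CSL627_1001 mix at entry, spread evenly over 10 to 50 and 50 to 100 EDs (midpoints 30 and 75); lead-in inhibitors occurring at the same rate and never counted.

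- Reading A, 100 EDs. Share of true risk still observable: Arm 3, 0.25 × 1; Arm 1, 0.75 × (0.31 × 0.70 + 0.39 × 0.25 + 0.30 × 0) = 0.75 × 0.315 = 0.24. Ratio to true incidence: 0.49.
- Reading B, 100 EDs. The 0.75 × 0.30 = 0.225 who entered past 100 leave the denominator: 0.49 / 0.775 = 0.63.

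A simulation of 2,000,000 subjects gave the same two ratios. Varying the Arm 1 share from 50% to 90%, the hazard (constant or front-loaded with mean 25 EDs) and the entry mix (with or without CSL627_3002) gave these ratios of planned to true incidence:

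| | 10 EDs | 50 EDs | 100 EDs |
|---|---|---|---|
| Reading A | 0.10–0.51 | 0.15–0.57 | 0.19–0.66 |
| Reading B | about 1.0 | 0.43–0.90 | 0.23–0.78 |

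**Step 4: the effect in the other direction.** The denominator omits inhibitor-free subjects who stop before the landmark. With dropout d, a true 2% becomes 0.02 / (0.02 + 0.98(1 − d)): 2.10%, 2.22% and 2.49% for d = 5%, 10% and 20%. This is smaller than the downward effect in these scenarios.

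**The case against.** The best defence is that the text does not commit to the harmful reading. SAP 4.7.1 says only the first dose, and SAP 4.7.4.2 and 4.7.7 apply its ED = 0 rule alongside a clock that starts in the pivotal study, so Reading C is possible. This stands as ambiguity. It does not settle the matter, because SAP 4.1.1.1 and 4.1.1.4 make this study the default and the SAP names the pivotal study where it means it.

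Second, a reader might infer that incidence is biased low by construction at all three landmarks. The documents do not support that. The not-tested exclusion may already remove rollovers who entered past a landmark, which leaves the 10-ED figure unbiased though resting on Arm 3. Dropout also pushes upward. Third, a reader might take 1.83% against 2.46% as the size of the bias. With zero events the estimate is 0% on either denominator, so these limits show precision only.

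The current-study summary helps only in part. Arm 1 samples are scheduled on cumulative EDs (Protocol 8.6.2), and the earliest exposure remains outside it. Cumulative EDs are indeed the prespecified design, but that argues for cumulative events as well.

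Finally, the PTP analysis is done: SAP 4.1.2 says so, and the SAP's change list dates the PTP report to November 2019. That limits urgency. However, SAP section 1 covers the final complete report and the PTP rules are still in it.

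**Conclusion.** The concern holds under the SAP's default baseline. Total-ED incidence at 50 and 100 EDs is then understated by delayed entry whenever lead-in inhibitors occurred, and the zero-event limit credits exposure in which no event could be counted. At 10 EDs the result is either low or rests almost wholly on Arm 3, which does not match an endpoint defined in at least 200 PTPs.

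The size cannot be determined from the documents. The simulated ratios depend on the stated assumptions, and the 52-of-200 illustration assumes that all 52 rolled over and were still counted. If no inhibitor arose in the lead-in studies, the point estimate is unharmed and pooling would support the stated limit. A reader might also conclude that lead-in subjects who never enrolled must be added. That would go beyond the Safety population (Protocol 11.2.2, SAP 3.5.2) and is not needed to align the clocks. Selection of who rolled over would remain and should be stated as a limitation.

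**What to change.** In SAP 4.7.1, for Arm 1 subjects enrolled in this study:

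1. Set the inhibitor baseline at the first rVIII-SingleChain dose in the lead-in study.
2. Count lead-in inhibitor tests in the tested rule, and confirmed lead-in inhibitors in the numerator, so that EDs, baseline and events share one origin. This agrees with Protocol 11.1 and 11.3.3.2.
3. If lead-in results cannot be pooled, use a delayed-entry cumulative incidence on the ED scale, exclude from each landmark denominator the subjects who passed it before entry, and restate the confidence interval.

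Present the result as a corrected or supplementary analysis in the final complete report. The cost is SAP wording and some re-programming with lead-in data from the sponsor's own studies. The incidence or its upper limit may become less favourable.

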#### 4.5.2 Extent of Exposure to rVIII-SingleChain

The extent of exposure to rVIII-SingleChain will be summarized for the Safety, Efficacy and Surgery population overall and by modality.

The following variables will be used to characterize extent of exposure to rVIII-SingleChain:

- EDs in the current study as a continuous and categorical variable, as in [Section 4.5.1](#)
- Number of injections; and the total number of injections over all subjects
- Dose administered per injection (IU/kg); the unit of observation is the injection
- Total IU administered; the unit of observation is the subject.

CCI

In addition, a separate extent of exposure to rVIII-SingleChain analysis over the period of inhibitor development will be provided while subjects are inhibitor positive on PUPs.

#### 4.5.3 Compliance and Adherence

Compliance will be summarized for the Efficacy population.

Compliance will be defined in terms of:

- The prophylaxis schedule, i.e. “prophylaxis compliance”. This is applicable only to the prophylaxis regimen.
- The prescribed dose, i.e., “dose compliance”. This is applicable to both the on-demand and prophylaxis regimens.

Prophylaxis compliance will be derived as:

$100 * (\text{number of on-schedule prophylaxis injections}) / (\text{expected number of prophylaxis injections})$ .

Expected number of prophylaxis injections will be computed considering the cumulative length of periods in which the subject has prophylaxis injections and the assigned regimen in these periods. Periods during which the subject receives injections for reasons different than prophylaxis are excluded.

Prophylaxis compliance will be categorized as 0 to < 80%,  $\geq 80$  to  $\leq 120\%$ ,  $\geq 120\%$ . Subjects whose prophylaxis compliance is not between 80% and 120% will be addressed in the periodic review of protocol deviations to determine whether they should be classified as non-compliant to the prophylaxis regimen.

Dose compliance will be derived as:

$100 * (\text{number of doses within } \pm 20\% \text{ of the prescribed dose}) / (\text{number of doses})$ .

Dose compliance will be summarized as a continuous and categorized as 0 to < 80%,  $\geq 80$  to  $\leq 100\%$ . Subjects whose dose compliance is not between 80% and 100% will be addressed in the periodic review protocol deviations to determine whether they should be classified as non-complaint to prescribed dose.

Adherence will be defined as having dose compliance and prophylaxis compliance (where applicable) based on medical review and assessment of protocol deviations.

CCI

Compliance will also be summarized while subjects are inhibitor positive on PUPs.

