6.3 Treatment Compliance

Subjects will record in the eDiary the administered dose and time of the dose for any injection of rVIII-SingleChain including prophylaxis, on-demand, prevention, post-surgery treatment of bleeding episodes, and CCI (if applicable). In addition, subjects will bring all of their used and partially used vials of rVIII-SingleChain to the study site at every visit. Unused vials near expiration or with insufficient shelf life to cover time duration until next visit should be returned at next scheduled visit. Treatment compliance will be monitored by counting the number of returned vials and these results will be recorded in the Drug Accountability Log. rVIII-SingleChain use, as reported by the subject in the eDiary, will be reconciled to the returned vials.

To be regarded as compliant to **regimen**, a subject on prophylaxis will have no less than 80% and no more than 120% of the scheduled number of doses during the study period (ie, a subject on 3 times per week who was on study for 10 weeks should have no less than 24 and no more than 36 doses administered for routine prophylaxis).

To be regarded as compliant to **dose**, at least 80% of prophylaxis or bleeding episode treatments doses administered must be within $\pm 20\%$ of the prescribed dose, ie, a subject assigned to prophylaxis 3 times a week who was on the study for 10 weeks (30 prophylaxis doses) and, in addition treated 10 bleeding episodes (10 bleeding episode treatment doses) was prescribed 50 IU/kg and weighed 80 kg (4000 IU) should have no more than 8 doses outside 3200 to 4800 IU.

7 Contraindications, Permitted Therapies and Prohibited Therapies

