## 4.11 Changes in Conduct or Planned Analyses from the Protocol

Section 2.1 and 2.2: In the protocol, incidence of inhibitor formation to FVIII in Arm 2, PUPs is stated that would be performed on at least 50 PUPs. However, this condition has been removed. Given that patients that develop inhibitors may be withdrawn from the study early, they would not necessarily achieve 50 exposure days but we would definitely have to include them in the calculation. Therefore the text was adjusted to ensure the option to properly report the endpoint regardless of these circumstances.

CCI

Section 3.5.3: Efficacy Population definition has been changed removing the exclusive inclusion of subjects who do not have an inhibitor at any time point during the study.

CCI

Section 4.6.1 and 4.6.2.1: In the Annualized Bleeding Rate analysis it has been added that subjects with an efficacy evaluation period less than 8 weeks (56 days) will be excluded from the analysis to exclude bias due to short evaluation period.

Section 4.6.2.2: The analysis of number of infusions of CSL627 required to achieve hemostasis has been added for completeness of analysis.

Section 4.7.1: Incidence of transient inhibitors has been added for completeness of analysis.

Section 4.7.2.1: Analysis of AESIs has been added for completeness of analysis.

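### SAP 4.5.3 bases expected prophylaxis injections on periods that contain injections, so an untreated gap of more than 20% of scheduled time can escape the 80% to 120% limits of Protocol 6.3

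*SAP*

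**What the plan says.** **Protocol 6.3.** A subject on prophylaxis is compliant with the regimen if he has "no less than 80% and no more than 120% of the scheduled number of doses during the study period". The example is "a subject on 3 times per week who was on study for 10 weeks", who "should have no less than 24 and no more than 36 doses administered for routine prophylaxis". The dose-compliance example in the same section keeps 30 prophylaxis doses for 10 weeks although 10 bleeding episodes were also treated.

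**SAP 4.5.3.** Prophylaxis compliance is 100 times the on-schedule prophylaxis injections divided by the expected prophylaxis injections. The expected number is computed "considering the cumulative length of periods in which the subject has prophylaxis injections and the assigned regimen in these periods". The next sentence adds: "Periods during which the subject receives injections for reasons different than prophylaxis are excluded". Neither *period* nor *on-schedule* is defined, and no maximum gap is given.

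**Use of the result.** "Subjects whose prophylaxis compliance is not between 80% and 120% will be addressed in the periodic review of protocol deviations". Adherence requires dose compliance and, where applicable, prophylaxis compliance, "based on medical review and assessment of protocol deviations".

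**Declaration.** SAP 4.11 records other departures from the protocol, for example the entry that opens "In the Annualized Bleeding Rate analysis it has been added that subjects with an efficacy evaluation period less than 8 weeks". It has no entry for the compliance denominator. The SAP's list of substantial changes explains the second exclusion by the effect of other kinds of infusion. It gives no reason for leaving out time without injections.

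**The concern.** The protocol's denominator depends on what was scheduled. The SAP's depends on what was injected. A missed stretch of prophylaxis is what a compliance measure should detect, yet under the SAP wording it can shrink the numerator and the denominator together and leave the ratio unchanged.

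Two uses are at stake. The ratio is the numerical trigger for deviation review, so a subject scored inside the band is not sent there by this measure. Compliance also helps a reader judge bleeding rates reported during prophylaxis.

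The second exclusion raises a related question. The SAP places it with the expected count and does not say whether prophylaxis injections given in the excluded periods also leave the numerator. If they stay, the ratio is too high for subjects with more treated bleeds.

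**Working it through.** **Inputs.** Frequency 3 per week, 10 weeks, band 80% to 120% (Protocol 6.3). End of treatment at 75 exposure days for inhibitor-negative previously untreated patients and at least 100 for previously treated patients (Protocol 3.3). Gap length is an assumption, because the documents give none. All doses outside the gap are taken on schedule.

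**Step 1: reproduce the protocol example.** Scheduled doses = 3 × 10 = 30. Limits are 0.8 × 30 = 24 and 1.2 × 30 = 36, as stated.

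**Step 2: put a gap of g weeks into that example.** Protocol ratio = 3(10 − g)/30. SAP ratio, if weeks without injections drop out, = 3(10 − g)/[3(10 − g)].

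| Gap (weeks) | Protocol 6.3 | SAP read literally |
|---|---|---|
| 1 | 27/30 = 90% | 27/27 = 100% |
| 2 | 24/30 = 80% | 24/24 = 100% |
| 3 | 21/30 = 70% | 21/21 = 100% |
| 4 | 18/30 = 60% | 18/18 = 100% |

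**Step 3: the other reading.** If a period runs from first to last injection on a regimen, a 3-week gap in mid-course stays in the denominator (21/30 = 70%, as in the protocol). A 3-week stop at the end still drops out (21/21 = 100%).

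**Step 4: when the classification changes.** With W scheduled weeks, (W − g)/W falls below 0.80 only if g > 0.2W.

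| Scheduled weeks | Gap must exceed | Protocol score for a 4-week gap |
|---|---|---|
| 10 | 2 weeks | 60% |
| 25 | 5 weeks | 84% |
| 52 | 10.4 weeks | 92.3% |
| 260 | 52 weeks | 98.5% |

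If participation ends at a fixed number of exposure days, a gap lengthens the stay. With A weeks of injecting, W = A + g, and the condition becomes g > 0.25A. Taking one prophylaxis injection per exposure day:

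- 75 exposure days at 3 per week: A = 25, so g > 6.25 weeks.
- 100 exposure days at 3 per week: A = 33.3, so g > 8.3 weeks.
- 75 exposure days at 2 per week: A = 37.5, so g > 9.4 weeks.

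**Step 5: one-sided exclusion.** Suppose a fraction u of prophylaxis time is removed from the expected count and nothing is removed from the numerator. The ratio is then multiplied by 1/(1 − u). A subject who took every dose passes 120% when 1/(1 − u) > 1.2, that is, when u > 1/6. If both sides are cut, this inflation disappears. The documents do not fix u, because they do not say how long a period is.

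**Step 6: categories.** The middle category includes 120% and the top category starts at 120%, so a score of exactly 120% falls in both.

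**The case against.** The strongest reply is that *period* is undefined and that the same sentence ties periods to the assigned regimen. They may be meant as regimen intervals. Some restriction to prophylaxis time is needed, since regimens can be switched at any time and no prophylaxis doses are scheduled during on-demand treatment. This stands: the 100% score is one reading, not a certainty. It does not remove the point, because a stop at the end is lost on the first-to-last reading too, and a term that gives 70% or 100% for the same subject needs a definition.

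Four stronger inferences are tempting, and the documents do not support them.

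- *Stopping for some weeks is non-compliance under the protocol.* Only a gap above 20% of scheduled time is. A 4-week stop in 25 weeks scores 84%.
- *The ratio rises with every treated bleed.* This assumes that the exclusion touches the denominator only, which the SAP does not say. One could take one excluded day per bleed and the protocol example's 10 bleeds: 60 × 3/7 = 25.7 expected, so 30 doses score 116.7%. But one-day periods cannot be the rule in the sentence on periods with injections: 21 injection days would give 21 × 3/7 = 9 expected and 233%. The figure mixes two meanings of the term.
- *Lapses cannot show anywhere.* Annualised consumption divides by the whole efficacy evaluation period (SAP 4.6 and 4.6.2.3), diary use is reconciled with returned vials (Protocol 6.3), and all deviations are listed (SAP 4.9). Adherence also rests on medical review.
- *The efficacy results are affected.* Compliance does not define the Efficacy population (SAP 3.5.3) and does not enter the derivation of the annualized spontaneous bleeding rate (SAP 4.6.1.1).

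**Conclusion.** The concern holds within limits. The SAP changes the protocol's compliance denominator without declaring it in SAP 4.11, and as written the rule can score a subject as compliant whom Protocol 6.3 would class as non-compliant. In the protocol's example the difference is 70% against 100% for a 3-week stop. That rests on the literal reading, in which time without injections drops out. On the first-to-last reading only a stop at the end is lost.

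The classification changes only for gaps above 20% of scheduled prophylaxis time. The possible upward bias for subjects with more treated bleeds is conditional on a one-sided exclusion, and its size cannot be fixed from the documents. Because the measure is descriptive, the consequence is a missed trigger for deviation review and a compliance table that may flatter. It does not change an analysis population or a bleeding-rate estimate. It should be corrected because the rule can give a wrong classification and the repair is small.

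**What to change.** In SAP 4.5.3:

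- Define expected injections as the sum, over all time assigned to a prophylaxis regimen (regimen start to stop dates, including time without injections), of time multiplied by assigned frequency.
- Remove any excluded interval, such as a surgical period, from numerator and denominator alike.
- Define *on-schedule*, or count all injections recorded as routine prophylaxis, as Protocol 6.3 does.
- Make the top category strictly above 120%.
- State in SAP 4.11 or the study report whether the completed analysis of previously treated patients used the present rule.

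The cost is a few sentences and one derived variable. Protocol 3.2.5 already requires regimen changes to be recorded in the eCRF, and injections are recorded in the eDiary. The price is that compliance figures may be less favourable, and those for previously untreated patients may not be directly comparable with the report on previously treated patients, which the SAP's list of substantial changes gives as completed in November 2019.
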